Study Procedures	Patients who present to the ED at one of the two participating CHS EDs with a telepsychiatric consult performed will be treated and followed per the proposed CHS behavioral health patient navigation pathway (BH-VPN) or usual care. As part of the current care process, Patients are identified by the ED physician in the ED as needing psychiatric evaluation and a referral is made to the telepsychiatric consult, the care of these patients will follow the allocated BH-VPN pathway or

	
usual care. Regardless of participation in the BH-VPN pathway or usual care, the ED providers decide based on available information the ultimate disposition for patients --discharge from the ED or admit to the hospital.
 
Patients who complete a telepsychiatric consult in the ED Monday through Friday during the hours of operation can be enrolled to either the control or intervention arm based on a randomization scheme that randomly allocates days that navigators are available. On days where the navigator is available, all patients who meet eligibility criteria will be considered exposed to the interventions; whereas, on days the navigator is not available all patients will be considered exposed to Usual care. Patients who are in the intervention arm will be offered navigation services for 45 days following ED discharge.
 
The BH-VPN pathway is defined by several key components:
 
 
• Introduction of the navigation process to the patient, while in the ED
 
• Evaluation of the patient and their needs.
 
• Follow-up evaluation within 72 hours by phone, and weekly contact with the BH-VPN until 45 days post ED discharge
 
• Confirm that a follow-up visit is scheduled and if the patient made it to the appointment.
 
• Placement into an appropriate case management program, if needed
 

Statistical Analysis
	
Analyses will include all patients identified as having completed telepsychiatric consult and meeting the additional inclusion and exclusion criteria. Comparisons of the intervention and usual care groups will be made using univariate analyses such as the t-test and chi-square test. The primary outcome, ED to inpatient conversion, will be compared between the two groups of patients using logistic regression. Results will be presented with odds ratios and 95% confidence intervals.

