## 6.1. Sample size analysis and statistical analysis

We are conducting the study for about 6 months leading to approximately 6 months\*4 weeks\*5 days=120 days with 60 days allocated to intervention and 60 allocated to treatment as usual. This study is designed to detect a 15% absolute reduction in the inpatient admission within 5 days of index ED presentation with the usual care group assumed to have a 50% inpatient admission rate (internal report). We will have 85% power to detect this reduction with a total sample size of 414 ( $\alpha=0.05$ ) using a Chi-square test for independence. We will not need to adjust for attrition as the primary outcome of inpatient admission <5 days is obtainable from electronic health records for all individuals. To account for the possible correlation among patients seen in the ED on the same day, we have inflated the sample size by 10% assuming the average number of patients per ED per day is 2 and the intra-class correlation coefficient=0.1 (Design effect=1+(2-1)ICC). Therefore, our target sample size is N=456.

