## 6.2. Statistical analysis

All analyses will follow intention to treat such that patients will be analyzed based on the allocated intervention on the day of their ED visit (BH-VPN or treatment as usual). We will compare the two groups on age, sex, suicide ideation, and neurocognitive disorders to assess for balance, which is inferred with randomization.

The primary outcome, inpatient admission  $\leq 5$  days, will be compared between the two groups of patients using a chi-square test. We will explore differences by site by conducting stratified analysis by hospital. We will attempt to adjust for the correlation among patients seen on the same day using a generalized linear mixed model with a log link and random effect for day, nested within hospital. If convergence problems arise due to small sample sizes, we will collapse by week rather than day. We will also control for hospital as a fixed effect in the model. Results for group comparisons will be presented with odds ratios and 95% confidence intervals.

Secondary outcomes are 45-day post discharge utilization (yes/no), 90-day post discharge utilization (yes/no), QCC defined 30-day readmission (yes/no), and patient centric 30-day readmission (yes/no). Each of the secondary outcomes are dichotomous and will be compared using the same approach as the primary outcome. All tests will be two sided and the data will be analyzed using SAS Enterprise Guide version 6.1. For all outcomes, we assume if there are no visits in the CHS electronic medical record that the value for having a visit is null; therefore, there will be no missing data for the primary or secondary outcome measures.

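### Section 6.2 pairs a log-link mixed model with odds-ratio reporting; a log link gives risk ratios, and the Protocol Summary names logistic regression

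*Combined protocol and SAP*

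**What the plan says.** Section 6.2 first compares the primary outcome (admission within 5 days, yes/no) by a chi-square test. It then says the team will attempt to allow for correlation among same-day patients "using a generalized linear mixed model with a log link and random effect for day, nested within hospital", with hospital as a fixed effect. No distribution is given. If the model does not converge because of small samples, the random effect moves from day to week. The paragraph ends: "Results for group comparisons will be presented with odds ratios and 95% confidence intervals". The four secondary outcomes, all yes/no, follow the same approach.

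The Statistical Analysis row of the Protocol Summary differs: "The primary outcome, ED to inpatient conversion, will be compared between the two groups of patients using logistic regression". It also promises odds ratios with 95% confidence intervals. Neither place mentions a risk ratio.

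**The concern.** For a binary outcome, the link decides what the exponentiated treatment coefficient means. With a log link it is a ratio of risks; with a logit link it is a ratio of odds. The model in Section 6.2 therefore does not produce the effect measure that the same paragraph promises, whereas the Summary's model does.

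Two things are at stake. First, the analyst must settle the conflict alone, possibly with the data in view, and each choice departs from some part of the text. Second, if the model is fitted as written and its output labelled as the text says, a risk ratio is published as an odds ratio. With an event rate near 50%, the two are far apart.

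**Working it through.** **Inputs.** From Section 6.1: "usual care group assumed to have a 50% inpatient admission rate"; "designed to detect a 15% absolute reduction in the inpatient admission", hence 50% against 35%; "We will have 85% power to detect this reduction"; "total sample size of 414 ( $\alpha=0.05$ ) using a Chi-square test for independence"; intra-class correlation 0.1; 60 days per arm; target N = 456. From Section 6.2: "All tests will be two sided".

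**1. The plan's own figure.** Two-proportion formula, pooled rate 0.425:

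n = [1.960 × √(2 × 0.425 × 0.575) + 1.036 × √(0.50 × 0.50 + 0.35 × 0.65)]² / 0.15² = 193.5 per arm.

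With continuity correction: (193.5/4) × [1 + √(1 + 4/(193.5 × 0.15))]² = 206.6, so 207 per arm and 414 in total, as stated. Then 414 × 1.1 = 455.4, rounded up to 456. This rests on a chi-square test, so the choice of link does not touch it.

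**2. The two scales at the design rates.**

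- Risk ratio (log link): 0.35/0.50 = 0.70.
- Odds ratio (logit link): (0.35/0.65)/(0.50/0.50) = 0.54.

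These are population-level values. A logit model with a random day effect estimates a day-specific odds ratio, which lies somewhat further from 1.

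**3. If 0.70 is read as an odds ratio.** Control odds are 1, so the implied intervention rate is 0.70/(1 + 0.70) = 41.2%. The implied reduction is 50 − 41.2 = 8.8 points instead of 15, which is about 41% too small.

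**4. Precision at 228 per arm, ignoring clustering.**

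- SE of log risk ratio = √(0.65/79.8 + 0.50/114) = 0.112, giving a 95% CI of 0.56 to 0.87.
- SE of log odds ratio = √(1/79.8 + 1/148.2 + 1/114 + 1/114) = 0.192, giving 0.37 to 0.78.

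Both intervals exclude 1.

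**5. Secondary outcomes.** The gap shrinks as events become rarer. Section 2 cites a 7% system readmission rate. If that applied to the 30-day readmission outcomes (an assumption), a risk ratio of 0.70 gives 4.9%, and the odds ratio is (0.049/0.951)/(0.07/0.93) = 0.68. No rates are given for 45- or 90-day utilization.

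**6. The upper bound on probability.** A log link with a normal day effect does not keep probabilities below 1. With ICC 0.1 at a rate of 50%, the day-level variance is 0.1 × 0.25 = 0.025 (SD 0.158).

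- Taking 50% as the median, with log SD 0.158/0.5 = 0.316: P(Z > 0.693/0.316) = 1.4%.
- Taking 50% as the mean: log variance ln(1.1) = 0.0953, SD 0.309, log median −0.693 − 0.048 = −0.741, and P(Z > 0.741/0.309) = 0.8%.

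At 0.8%, that is about one of the 60 × 2 = 120 usual-care hospital-days.

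**7. Does the model fail to converge?** Sixty trials were simulated per scenario: 120 days, two hospitals, 1.9 patients per hospital-day on average. Each was fitted as a binomial mixed model by pseudo-likelihood. Log-link failures:

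- ICC 0, equal hospitals: 0/60
- ICC 0.05: 2/60
- ICC 0.1, equal hospitals: 4/60
- ICC 0.1, control rates about 57% and 43% by hospital: 0/60
- ICC 0.1, control rates about 65% and 38% by hospital: 25/60

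The logit link failed in 0/60 in every scenario. The hospital-specific rates, beta-distributed day effects, Poisson daily counts and fitting routine are assumptions outside the documents; SAS may behave differently.

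**The case against.** The strongest defence is that log is a slip for logit. The odds-ratio sentence and the Summary's logistic regression both point that way, so the analyst may well fit the right model. This is plausible, but it amounts to saying that the text should be corrected.

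Three stronger readings are tempting, and the documents do not support them.

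- **That this model is the settled primary analysis.** Section 6.2 names the chi-square test first, Section 6.1 sizes the trial on it, and the mixed model is introduced as an attempt at adjustment. No section says which result leads. On the other side, allocation is by day (Section 5.2), and the mixed model is the only analysis in Section 6.2 that allows for that clustering.
- **That the published effect will be mislabelled.** This happens only if the log-link coefficient is fitted as written and printed as an odds ratio. The odds ratio could instead come from the 2×2 table or from the Summary's logistic regression. Mislabelling at the design rates would understate a benefit. It would not create a false positive, and the chi-square test would be untouched.
- **That the model is prone to fail at a 50% event rate.** At the plan's rate, failures ran from 0 to 7% of simulated trials unless the hospitals differed widely, and the documents give no hospital-specific rates. The argument also presumes a binomial distribution, which Section 6.2 does not state. A Poisson working model with log link has no upper bound of 1, though it too would give risk ratios.

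Keeping the log link and reporting risk ratios would also be coherent. It would, however, mean changing the reporting sentence and the Summary as well.

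**Conclusion.** Wrong as written; should-fix. The contradiction is on the page and needs no assumption: a log link for a yes/no outcome, no stated distribution, odds ratios promised in the same paragraph, and logistic regression in the Summary. At the design rates, the choice of scale is the difference between 0.70 and 0.54. The misreading of 8.8 points for 15 depends on the log-link estimate being labelled an odds ratio.

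The secondary outcomes inherit the wording, but not necessarily the size of the discrepancy, which would be trivial if readmission were near 7%. The upper-bound problem is a minor further reason to prefer logit. Moving the random effect from day to week would not remove it, but frequent non-convergence at the plan's rates is not shown.

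**What to change.** In Section 6.2, replace the log link with a binomial distribution and logit link, for the primary and the four secondary outcomes. The model then yields the promised odds ratios and agrees with the Summary's logistic regression.

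State in both places whether this mixed logistic model or the chi-square test is the headline analysis and which one supplies the reported odds ratio and interval. The link correction alone does not settle that.

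Optionally, report the model-standardised risk difference with its 95% CI beside the odds ratio, because Section 6.1 sizes the trial on an absolute reduction. This is a useful addition, not part of the error.

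The cost is a short wording change in Section 6.2, one clarifying sentence in each place and, if wanted, one extra line of output. No new data are needed, and N = 456 stands.

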The Hospital Improvement Innovation Network (HIIN) is a nationwide effort to reduce preventable hospital acquired conditions and hospital readmissions. Part of the HIIN effort surrounding behavioral health patients, includes identifying packages or key components most effective at preventing psychiatric admission and exploring ways to efficiently apply effective strategies. As a complement to the telepsychiatry program, a partnership has been formed with HIIN to develop a patient navigator program to provide short-term follow up to patients who are evaluated by telepsychiatry and potentially eligible for discharge home. The patient navigator will connect with the patient virtually prior to discharge from the ED and assist the patient in obtaining services and overcoming any barriers for 45 days post ED discharge.

By providing this wrap-around service to complement Carolinas HealthCare System's telepsychiatry program, we expect to decrease the number of patients admitted for inpatient psychiatric treatment and increase the number of discharges from the ED by providing another layer of service to our providers and patients. Additionally, we aim to decrease hospital inpatient admissions and increase after-care compliance with medications and appointments through short-term follow up. In one study regarding inpatient psychiatric care, it was found that patients who did not comply with at least one outpatient appointment after discharge were two times more likely to be readmitted than those who kept at least one appointment after discharge.

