## **4.4. Evaluable Population**

Patients included in the evaluable population for this project, will have their data inform the final outcomes assessment. All patients who meet the inclusion criteria and have a completed telepsychiatric consult will be assessed. Evaluation will be by intent to treat. All patients in the both arms will be assessed for the primary outcome. Patients admitted directly from the ED or have neurocognitive disabilities from the intervention arm will not receive services from the BH-VPN. Patients in either arm have the following potential disposition: (admission to the hospital for medical reasons, admission to a behavioral health facility by voluntary or involuntary commitment, discharge from the ED, or death).

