## **5. OVERALL DESIGN**

### **5.1. Outcome Variables**

#### **5.1.1. Primary Outcome Variable**

The primary outcome variable is ED to inpatient or observation conversion. This is a patient that presents to either of the two CHS ED sites and then within 5 days of their ED discharge are admitted for any reason to a CHS facility as an inpatient or observation patient. In the electronic medical record, 2 hospital encounters are shown, the ED encounter and the inpatient\observation hospital encounter. Based on data from 2016 at CHS, most patients discharged from the ED who convert to an admission do so within 2 days of their ED discharge. Five days were chosen to maximize the conversions attributed to the ED encounter.

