### **6. DATA COLLECTION AND REPORTING**

Patient demographics, comorbid conditions, and utilization will be obtained from the electronic medical record and billing systems. Data from the initial assessment and follow-up contacts will be stored in HealtheCare, a care management platform in Cerner. Data will be retrieved by an application specialist on the research team. Data may be retrieved retrospective to a patient's completion of the intervention or usual care arm of the study. A monthly executive summary will be produced, showing patient volume, percent patients with suicidal ideation, and utilization.

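### A patient committed from the index ED to a non-CHS facility would be scored as not converted, because the primary endpoint sees only CHS encounters and codes no CHS record as no event

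*Combined protocol and SAP*

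**What the plan says.** - **Endpoint (5.1.1).** A conversion is a patient who, within 5 days of ED discharge, is "admitted for any reason to a CHS facility as an inpatient or observation patient". The section adds that a conversion shows as two encounters in the record: the ED encounter and the hospital encounter.
- **No-record rule (6.2).** For all outcomes, "we assume if there are no visits in the CHS electronic medical record that the value for having a visit is null". The section concludes that "there will be no missing data for the primary or secondary outcome measures". Section 6.1 likewise makes no allowance for attrition.
- **Dispositions (4.4).** In either arm these are admission for medical reasons, "admission to a behavioral health facility by voluntary or involuntary commitment, discharge from the ED, or death". The behavioral health facility is not described as CHS or non-CHS.
- **Data source (6).** Demographics, comorbidity and "utilization will be obtained from the electronic medical record and billing systems". No outside source is named, and neither ED disposition nor destination is listed as a variable.
- **Aim (2).** The sponsor writes that "we expect to decrease the number of patients admitted for inpatient psychiatric treatment". The hypothesis in 1.1 is not limited to CHS either.

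**The concern.** The trial asks whether navigation lets more patients leave the ED without being admitted. A patient committed from the index ED to an outside psychiatric hospital is a clear conversion, yet generates no second CHS encounter. Under 5.1.1 and 6.2 that patient takes the same value as one sent home.

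This differs from the ordinary limit of single-system data, where later visits elsewhere go unseen. Here the missed event is the index disposition itself, which the participating ED decides. Saying that no outcome data are missing hides the gap. If many admissions go outside CHS, the endpoint measures admission to CHS rather than admission, the absolute difference is diluted, and a reader cannot tell fewer admissions from more transfers out.

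**Working it through.** **Tracing patients through 5.1.1 and 6.2**

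- Admitted to a CHS facility within 5 days: event, including a patient who later dies.
- Sent home, no CHS return: no event.
- Committed from the index ED to a non-CHS facility, no CHS encounter in the window: no event.
- Dies before any CHS admission: no event.

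The second and third lines receive the same value. No section provides a rule that separates them.

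**Reproducing the planned sample size**

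Inputs from 6.1 and 6.2: p1=0.50, p2=0.35, two-sided alpha 0.05, power 85%, equal allocation, design effect 1.10. Let d=p1−p2, and let p̄ be the mean of p1 and p2.

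- Uncorrected n per arm = [1.960√(2p̄(1−p̄)) + 1.036√(p1(1−p1)+p2(1−p2))]²/d² = (1.370+0.716)²/0.0225 ≈ 193.5.
- With continuity correction: (193.5/4)[1+√(1+4/(193.5×0.15))]² ≈ 206.6, so 207 per arm and 414 in total.
- 414×1.10 = 455.4, so 456.

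Both planned figures reproduce. The arithmetic is sound; the question is what counts as an event.

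**Effect of uncounted admissions**

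Assumptions: 50% and 35% are all-facility rates, and the same share f of admissions goes outside CHS in each arm. The documents do not give f, so a range is shown. Observed rates are 0.50(1−f) and 0.35(1−f), and the difference is 15(1−f) points. Power inverts the corrected formula at n=207: with m=n(1−1/(nd))², power = Φ{[d√m − 1.960√(2p̄(1−p̄))]/√(p1(1−p1)+p2(1−p2))}.

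At f=20%, d=0.12 and m=190.7, so (1.657−1.313)/0.6645 = 0.518 and power is 69.8%.

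| f | Observed rates | Difference (points) | Odds ratio | Power at 414 | N for 85% power (×1.10) |
|---|---|---|---|---|---|
| 0 | 50.0% vs 35.0% | 15.0 | 0.538 | 85% | 414 (456) |
| 10% | 45.0% vs 31.5% | 13.5 | 0.562 | 78% | 492 (542) |
| 20% | 40.0% vs 28.0% | 12.0 | 0.583 | 70% | 590 (649) |
| 40% | 30.0% vs 21.0% | 9.0 | 0.620 | 51% | 884 (973) |

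Without the continuity correction the powers are 87%, 81%, 73% and 56%. Section 4.1 expects 500 patients in 6 months, so under these assumptions f=10% already requires more than the expected accrual.

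**If the 50% is already CHS-only**

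The observed rates stay at 50% and 35% and power stays at 85%. The implied all-facility rates are 0.50/(1−f) and 0.35/(1−f), for example 62.5% vs 43.75% at f=20%. The planning figure is then consistent with the endpoint, but outside commitments are still coded as non-events.

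**The case against.** CHS-only capture is stated openly and suits a pragmatic evaluation. No section says that commitments leave CHS, so f may be negligible. The 50% comes from an internal report, so it may well be CHS-only, in which case the power loss above falls away. Equal f also leaves the risk ratio at 0.35/0.50 = 0.70. All of this stands. It limits the size of the problem but does not supply the missing rule.

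Three stronger readings are tempting, and the documents do not support them.

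- **That the trial would show a false benefit.** As an illustration only, suppose true admission is 50% in both arms, with f=10% in control and 20% in intervention. The observed rates are 45% and 40%, a spurious 5 points, with about an 18% chance of significance in favour of the intervention at N=414 (nominal 2.5%; no continuity correction or clustering). Swapping the shares reverses the sign. Nothing in the documents suggests such a split. Bed availability that varies from day to day adds chance variation, because days are randomized (5.2). Bias needs allocation itself to change where admitted patients go. Providers are told of the scheme (9.1), so this is possible. But the navigator approaches only patients recommended for discharge (5.3), and patients admitted directly receive no navigation (4.4).
- **That power is in fact lost.** This holds only if the planning rates cover all facilities, which 6.1 does not say.
- **That deaths are broadly scored as successes.** Only death before any CHS admission in the window is affected. No frequency is given, and section 5.1.4 already allows deaths to be compared by arm for safety. Whether death belongs in an admission endpoint is a matter of choice.

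**Conclusion.** The point holds as a gap in the primary endpoint's definition. Read together, 5.1.1 and 6.2 score an index-ED commitment or transfer to a non-CHS facility as no conversion, while 4.4 leaves such a disposition open and the trial's aim is to reduce it. That much follows from the text alone.

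The size cannot be fixed from the documents. It rests on f, which is unknown, and on whether the 50% is an all-facility rate. If it is, and f is equal by arm, the table gives the dilution and power loss. If it is CHS-only, only the misclassification remains. Systematic bias is possible but not shown.

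**What to change.** - **5.1.1:** count as a conversion any index-ED disposition of admission, commitment or transfer to an inpatient facility, CHS or not, as well as any CHS inpatient or observation admission within 5 days of ED discharge.
- **6.2:** for the primary outcome, treat no CHS record as no event only when the index disposition is not an admission, commitment or transfer to an inpatient facility. Remove the statement that no data are missing.
- **Sensitivity analysis:** report the CHS-only endpoint alongside.
- **Tabulation:** show index disposition by arm using the 4.4 categories, including death. This also reveals whether f is small and whether it differs by arm.
- **6.1:** state whether the 50% planning rate is CHS-only or all-facility.
- **Limitation:** state that admissions to non-CHS hospitals after ED discharge are not captured.

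The cost is protocol wording plus extraction of disposition and destination from the ED record. Section 6 does not list these as variables, so their availability must be confirmed. No new patient contact is needed.
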